COVER PAGE FOR PROTOCOL AND STATISTICAL ANALYSIS PLAN

Official Study Title: A Randomized Controlled Trial for Optimal Feeding Tube Placement

NCT number: NCT

IRB Approval Date: 11-21-17

Unique Protocol ID: HSC20170704H

Protocol Form: A Randomized Controlled Trial for Optimal Feeding Tube Placement

Item 1 UTHSCSA Tracking Number	HSC20170704H
---------------------------------------	--------------

Item 2 Abstract / Project Summary	
Provide a succinct and accurate description of the proposed research. State the purpose/aims. Describe concisely the research design and methods for achieving the stated goals. This section should be understandable to all members of the IRB, scientific and non-scientific.
 
DO NOT EXCEED THE SPACE PROVIDED.

--	---

Purpose/Objectives: Define the optimal method to place an enteral feeding tube. Our objective is to perform a randomized controlled trial of two different methods of tube placement with outcomes of cost, safety, radiation exposure, and the time.

Research Design/Plan: A randomized controlled trial comparing current standard blind method to CORTRAK enteral access system (CEAS), an FDA approved electromagnetic device to place enteric tubes.

Methods: Patient population would include patients in pediatric intensive care unit, pediatric cardiac unit, intermediate medical care unit and pediatric floor who receives postpyloric feeding tube placements. We are going to monitor total time and number attempts required for each successful placement, correlation of findings on x-ray versus CEAS, cost-effectiveness of this new equipment with standard blind method and decrease in radiation exposure with CEAS.

Clinical Relevance: For insertion of post-pyloric tube, standard blind technique is the most commonly used method. We plan to compare this routine methods with another FDA approved method of feeding tube placement using electromagnetic guidance. Our goal will be to determine if the electromagnetic method decreases the number of attempts, duration of time, and the number of x-rays needed to place a feeding tube. Recent retrospective adult and pediatric studies document promising results with minimal complications using this technique.

Item 3 Background	

Describe past experimental and/or clinical findings leading to the formulation of your study.
 
For research involving unapproved drugs, describe animal and human studies.
 
For research that involves approved drugs or devices, describe the FDA approved uses of this drug/device in relation to your protocol.
	
Insert background: Children admitted to PICU are undernourished 40-60% of times due to poor feeding tolerance. Critical illness is a catabolic stress state and nutritional requirements are much higher. Primary methods of nutrition delivery are parenteral nutrition (PN) and enteral nutrition(EN). Enteral feeding is preferable whenever possible as it is more physiological and more cost-effective without the added risk of nosocomial infection inherent with parenteral nutrition (PN). Two major routes of enteral nutrition are gastric feeding and postpyloric feeding. Because postpyloric EN reduces gastric residue, it reduces the risk of pulmonary aspiration and aspiration pneumonia. Postpyloric feeding has been shown to be associated with significantly lesser risk of pneumonia and vomiting as well as increased in total percentage of nutrition delivered compared to gastric tube feeding in critically ill patients. From our review of last 6 months' patient charts in last 6 months, there were 85 incidences of postpyloric feeding tube placement in 46 patients and total 194 x-rays were done to confirm placement, averaging 2.3 X-rays per placement attempt.

Item 4 Purpose and rationale	
Purpose: We hypothesize that enteric feeding tube placement under electromagnetic guidance using CEAS (Cortrak Enteral Access System) is superior to current standard blind technique. We wish to expand on previous studies to conclusively define that CEAS decreases number of attempts, total time and radiation exposure required during an accurate postpyloric feeding tube placement.
 
Rationale: Previous studies have conclusively shown that standard blind technique is associated with higher number of attempts, longer total time duration and more x-rays for confirmation as compared to CEAS. None of the

	
previous studies have been randomized though. We are planning to carry out a randomized controlled trial to evaluate CEAS more reliably and nullify population bias if any.
 
October et al, Pediatr Crit Care Med 2009 Vol. 10, No. 2: Successful placement of postpyloric enteral tubes using electromagnetic guidance in critically ill children.
 
Brown et al, American Journal of Critical Care, May 2017, Volume 26, No. 3: Use of electromagnetic device to insert postpyloric feeding tubes in a pediatric intensive care unit
 
Goggans et al, Nutrition in Clinical Practice Volume 32 Number 2 April 2017 233 – 237, Transpyloric Feeding Tube Placement Using Electromagnetic Placement Device in Children

--	--

Item 5 Study Population(s) Being Recruited
 
In your recruitment plan, how many different populations of prospective subjects do you plan to target? Provide number: 100
 
e.g., a population can be individuals with type 2 diabetes controlled with diet and/or a population of healthy controls. Or a population can be individuals attending an education program, etc.
 
List each different population on a separate row and provide a short descriptive label: (e.g., normal-healthy, diabetics, parents, children, etc.)
 
To add rows use copy & paste
	
Identify the criteria for inclusion:
	
Identify the criteria for exclusion:

 - Children admitted to pediatric Floor, IMC, PICU and pediatric cardiac ICU who need a postpyloric feeding tube 	
 - Patient admitted to pediatric floor, IMC, pediatric ICU or pediatric cardiac ICU requiring postpyloric feeding tube placement of size 8F or more and not meeting any of exclusion criteria 	
 - Open chest wall - Open abdominal wall

Item 6 Research Plan / Description of the Research Methods a. Provide a comprehensive narrative describing the research methods. Provide the plan for data analysis (include as applicable the sample size calculation).
	
uq	
Step-by-Step Methods: We intend to conduct a randomized controlled trial comparing current standard blind technique to CORTAK enteral access system (CEAS), the electromagnetic device to place enteric tubes. Both techniques are FDA approved and being used across the country. University hospital has recently purchased the CEAS and we have already used it to placed feeding tube in children. CEAS uses same feeding tube that is currently being used at UHS,. The stylet used with CEAS has a small magnetic tip to generate a signal captured by the receiver placed on the patient’s lower chest.. Receiver is connected to a monitor which shows the path of feeding tube as it advances during insertion. Blind technique uses the same tube and same stylet except the

nurse places the tube by moving the patient around.

When a patient in pediatrics needs a post pyloric feeding tube, we approach the parents to explain the need for adequate nutrition in safe manner. After the clinical discussion, the parents will be informed that we are comparing 2 different methods of placement to determine which one can be completed with less attempts and x-rays to confirm placement. As previous studies have documented safety and efficacy of this technique we will be performing a prospective randomized trial. Patients will be randomized using sealed envelopes in a locked box, prepared by a person not part of this study. We are planning to form a team of total 11 nurses (covering both day and night shifts) to be the super users for feeding tube placement. Each member will be trained with the new equipment for a period of 1-2 weeks before getting involved in the study. The identity of the nurses inserting feeding tube will not be collected. Feeding tube placement will occur per randomization. Regardless of method used, per local clinical practice, a chest xray is obtained to verify placement. If the tube is not shown to be placed correctly (regardless of the placement method), the tube will be repositioned, and another xray is taken until confirmation is obtained that the tube is in proper place. Data collection sheet (attached with this form), monitoring total time and attempts required, will be completed for every participant. An enrollment log will match a unique identifier assigned to each participant with their demographic information. All data will be entered and maintained on UTHSCSA REDCap server the remaining information (e.g., enrollment log and data sheet) will be in locked cabinet. Each successful placement will be considered 1 event. After placement if the feeding tube comes out accidentally or the child pulls it out, child will go through the randomization process again for repeat placement and new event will be considered as a new subject. At the time of analysis, we will carry out separate analysis for all subjects with initial placement and repeat placement. We are also going to monitor correlation of findings on x-ray versus CEAS and how closely CEAS predicts correct location confirmed by an x-ray post-placement. We will compare cost-effectiveness of this new equipment with standard blind method. We are going to analyze if using CEAS brings radiation exposure down significantly for enteric tube placement. If statistically significant, we will start a separate study to analyze if CEAS can be substitute for x-ray confirmation and if the current practice of x-ray confirmation can be discontinued. Device has the FDA clearance for feeding tube placement without an X-ray confirmation. Concurrently, we will gather clinical data on secondary outcomes that include intensive care unit stay, hospital stay, mechanical ventilation days, reason for admission and time to achieve full feeds, previous gastrointestinal (GI) procedures or surgeries.

Data Analysis Plan: We will make all attempts to standardize the patients within each group. Meaning, we recognize that a healthy child with no significant past medical history may not be comparable to a child with caustic ingestion or a child with history of esophageal stricture or previous esophageal surgeries or a child with severe scoliosis. Within each of the groups of standard blind technique and CORTRAK Enteral Access System (CEAS) patients, we will index the results to the Pediatric Risk of Mortality (PRISM) score. To determine the difference between the two methods we performed a power analysis on our hypothesis that CEAS method will decrease radiation exposure, time to placement, and cost compared to the blind technique. The standard (two-sided) F-test of association between CEAS and blind technique placement will yield a power of 86% given 40 subjects with a Type I error of 0.05. We made this power calculation using PASS 2008 (NCSS, LLC. Kaysville, Utah). For each of the populations we are interested we will enroll a minimum of 100 individuals. At 30 patients, we will perform a mid-study analysis to decide how long the study needs to continue.

Item 7 Risks Section:

Complete the following table to describe the risks of all **research procedures** listed in Step 2, Institutional Form (items 28-34). *Do not list risks of Routine care procedures here.*

N/A, Risks are described in the informed consent document – do not complete this table.

Research procedures
 
example:
 
 • History and physical • Questionnaire • Laboratory tests 
Add or delete rows as needed
	
Risks
 
List the reasonably expected risks under the following categories as appropriate:

Placement of device over child's chest and abdomen
	
Serious and likely;  none Serious and less likely;  none Serious and rare;  none  Not serious and likely;  none Not serious and less likely  none


Insertion of a feeding tube (no difference between both procedures)
	
Serious and likely;  none Serious and less likely;  none Serious and rare;  Perforation of bowel  misplacement into lungs leading to pneumonitis Not serious and likely;  Discomfort to the child Not serious and less likely  none

Data collection
	
Serious and likely;  none Serious and less likely;  none Serious and rare;  none Not serious and likely;  none Not serious and less likely  Confidentiality breach

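### Does counting events by successful placement, without naming the x-ray film, undermine the randomised comparison?

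*Combined protocol and SAP*

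**What the plan says.** Item 6 (Step-by-Step Methods) defines the unit: "Each successful placement will be considered 1 event". The next sentence deals with a tube that later comes out: the child is randomised again and the repeat counts as a new subject. Initial and repeat placements are then analysed separately, each for all subjects concerned. The Abstract (Item 2) lists "total time and number attempts required for each successful placement" among the quantities monitored. The hypothesis in Item 4 is that "CEAS decreases number of attempts, total time and radiation exposure required during an accurate postpyloric feeding tube placement".

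On conduct, Item 6 says "Feeding tube placement will occur per randomization". A tube not shown to be in place is repositioned, whichever method was used, and "another xray is taken until confirmation is obtained that the tube is in proper place". A data sheet recording time and attempts is filled in for each participant.

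On agreement, Item 6 plans to examine "correlation of findings on x-ray versus CEAS and how closely CEAS predicts correct location confirmed by an x-ray post-placement". Directly after the sentence on radiation exposure it adds "If statistically significant, we will start a separate study to analyze if CEAS can be substitute for x-ray confirmation".

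**The concern.** Taken literally, an event exists only once a placement succeeds. A randomised placement that was abandoned, switched to the other method or never confirmed would then have no place in the analysis. Restricting the comparison to successes conditions on something that happens after randomisation and may differ by arm. That would weaken the trial's main advance, since Item 4 notes that no earlier study was randomised. No intention-to-treat statement or failure category appears in the Data Analysis Plan to prevent it.

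The film question looks like a second gap. Item 3 implies more than two films per placement, yet the comparison refers only to an x-ray after placement. Filming continues until position is confirmed, so the last film of a completed placement always shows a correct position. Pairing CEAS with that film could never reveal a CEAS reading of correct that an earlier film had refuted. Such false readings are what a later study of CEAS as a substitute for x-ray would most need to know about.

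**Working it through.** **The plan's own figure.** Item 3 reports "85 incidences of postpyloric feeding tube placement in 46 patients and total 194 x-rays were done to confirm placement". 194/85 = 2.28, which agrees with the stated average of 2.3.

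**What the text implies.** Under Item 6 as written, each placement is made by its assigned method and filming ends only at confirmation. Every randomised placement then becomes a successful one, the two analysis sets are the same, and the ratio of the success-only to the all-randomised difference is 100%. A departure needs an event that the plan does not describe.

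**If that event occurred.** The documents give no failure rate, so everything below is illustrative. Assumptions: each film is one attempt with a constant chance p of confirmation (q = 1 − p); blind p is solved so that the all-randomised mean is 2.28 films; CEAS p is 0.6 to 0.8.

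*(a) Abandonment at a limit of c films, both arms.*
- Failures = q^c.
- Mean films, all randomised = (1 − q^c)/p.
- Mean films, successes only = [(1 − q^c)/p − c·q^c]/(1 − q^c).

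Worked case, c = 5:
- Blind p = 0.406, failures 7.4%; all randomised 2.282, successes 2.065.
- CEAS p = 0.70: all randomised 1.425, successes 1.416.
- Differences: 2.282 − 1.425 = 0.857 and 2.065 − 1.416 = 0.648 (from unrounded means). Ratio 0.648/0.857 = 0.76.

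| Film limit (assumed) | Blind p | Blind failures | Success-only difference as % of all-randomised (CEAS 0.6 to 0.8) |
|---|---|---|---|
| 4 | 0.368 | 15.9% | 60–69% |
| 5 | 0.406 | 7.4% | 71–79% |
| 6 | 0.422 | 3.7% | 80–86% |
| 8 | 0.434 | 1.1% | 91–94% |
| 10 | 0.437 | 0.3% | 96–98% |

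*(b) The same chance of abandonment after every failed film* (0.05 or 0.10; blind failures 6.7% or 14.2%). How a placement ends is then unrelated to how many films it took, so successes also average 2.28 and the ratio is 100%.

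*(c) Abandonment straight after a failed first film, blind arm only.*
- Chance 0.10: blind p = 0.412, failures 5.9%, mean among successes 2.362. With CEAS p = 0.6 (mean 1/0.6 = 1.667), the ratio is (2.362 − 1.667)/(2.282 − 1.667) = 1.13. For CEAS 0.7 and 0.8 it is 1.09 and 1.08.
- Chance 0.20: failures 12.3%, mean among successes 2.462, ratios 1.29, 1.21 and 1.17.

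The bias can therefore reduce the difference, leave it alone or enlarge it.

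**Power.** Simulated with 50 per arm (assumed) and a 5-film limit, a t-test on all randomised placements against one on successes only gives 97% against 89% for CEAS 0.70, and 75% against 53% for CEAS 0.60. These losses belong to that assumed limit.

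**Choice of film.** Suppose CEAS reads correct in 50 completed placements and the first film confirms 35 (assumed). First-film agreement is 35/50 = 70% (exact 95% CI 55–82%). Final-film agreement is 50/50 = 100% (93–100%) by construction. The choice would matter, so the question is which film the plan means. Item 6 first describes one film taken to verify placement and a further film only if that one fails. It then asks how closely CEAS predicts a location confirmed after placement. A prediction is naturally tested against the first verifying film.

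**The case for a change.** The best case for a change is that failures are foreseeable. The Data Analysis Plan itself mentions children with caustic ingestion, esophageal stricture, earlier esophageal surgery or severe scoliosis, and the exclusion criteria list only an open chest or abdominal wall. Both methods use the same tube and stylet, so finishing by the other method would be easy. Re-filming until confirmation describes the intended course and does not say how an exception is analysed. A rule written beforehand costs only wording, whereas one chosen after the results are seen is open to bias. The film question, moreover, arises even if nothing is abandoned.

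Some of this stands. No sentence states that placements are analysed as randomised, and none names the film. But silence about a contingency is not an instruction to exclude. The event sentence leads straight into the re-randomisation rule, the data sheet covers every participant, and the two named analyses take in all subjects. The ordinary way to fill the gap is to keep each randomised placement in its arm, count all its films, time and attempts, and report any failure by arm. The text allows this.

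A stronger remedy, a rank test placing failures below every success, is a debatable replacement for the planned F-test. In the 5-film illustration it costs power: 94% against 97% for CEAS 0.70, and 68% against 75% for CEAS 0.60.

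On the film, the follow-on study is triggered by the radiation result and would itself test substitution, so no decision in this trial depends on the pairing. The two worries also pull apart: the first needs placements that are never confirmed, while a final film that is always correct needs placements that are.

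**Conclusion.** No change is needed. The plan leaves two details unstated, and both have a sensible default that its wording supports: analyse every randomised placement in its assigned arm, and compare the CEAS reading with the first film taken to verify it. If the trial runs as Item 6 describes, the effect on the arm comparison is zero.

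If unconfirmed placements occurred and were dropped, the x-ray difference could be 60% to 129% of its all-randomised value. That range rests entirely on assumed film limits, abandonment patterns and CEAS success rates, and it does not fix even the direction of the error. Asking how closely CEAS predicts the x-ray location already calls for the share of CEAS readings of correct that the film confirms.

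The conclusion assumes that Item 6 is followed and that analysts keep any exceptional placement in its arm. The data collection sheet is attached to the form but is not in the supplied text, so it may already record failures and film-by-film readings.

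### Re-randomised repeats count as new subjects, and the repeat-placement analysis has no rule for child-level stay outcomes or for several placements in one child

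*Combined protocol and SAP*

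**What the plan says.** The rules are in Item 6, Step-by-Step Methods:

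- "Each successful placement will be considered 1 event".
- If the tube is lost, the "child will go through the randomization process again for repeat placement and new event will be considered as a new subject".
- At analysis, "we will carry out separate analysis for all subjects with initial placement and repeat placement".
- Clinical data will be gathered on "secondary outcomes that include intensive care unit stay, hospital stay, mechanical ventilation days", together with time to full feeds. No time origin is given, and nothing limits these outcomes to the first placement.

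Item 6, Data Analysis Plan, names a two-sided F-test and indexing to PRISM. Neither is a within-child method. The counts there use three different nouns. On power, the test "will yield a power of 86% given 40 subjects with a Type I error of 0.05". The interim look is set in patients: "At 30 patients, we will perform a mid-study analysis to decide how long the study needs to continue". The enrolment target, by contrast, is worded in another unit: "For each of the populations we are interested we will enroll a minimum of 100 individuals".

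Item 3, Background, shows that repeats were common locally: "there were 85 incidences of postpyloric feeding tube placement in 46 patients".

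**The concern.** The plan's unit is the placement, but ICU stay, hospital stay and ventilator days belong to the child or the admission. If the counting rule is followed in the repeat set, two things happen to stay. A child with several repeats enters the same stay several times, possibly under both arms. And, on the plain meaning of stay, days that passed before the repeat are counted toward an arm that had not yet been drawn. A comparison of stay by arm could then show nothing when an effect exists, and a reader could take that as evidence of no benefit.

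For time, attempts and X-rays the placement is the right unit. Even so, a child's repeats are likely to resemble one another, and an ordinary F-test on subjects treated as unrelated makes no use of that. What is at stake is the interpretation of secondary outcomes and the precision of the repeat analysis.

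**Working it through.** **1. The plan's power figure.** The 86% cannot be reproduced because no effect size or SD is given. Solving the two-group F-test for 86% (alpha 0.05, 1:1 allocation assumed) gives a standardised difference of 0.987 if 40 is the total and 0.688 if 40 is per arm. The point does not depend on this figure.

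**2. How many repeats.** From Item 3: 85 − 46 = 39 repeats, and 39/85 = 45.9%. Applied to 100 placements (an assumption): 100 × 46/85 = 54.1 first placements and 45.9 repeats, rounded to 54 + 46. A mix with fewer repeats, 80 + 20, is also assumed.

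**3. Children with two or more rows in the repeat set.** The documents do not say how repeats spread over children. Assume that every way of spreading r repeats over n children is equally likely. The expected number with two or more repeats is then n × r(r−1) / [(n+r−1)(n+r−2)].

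- 54 + 46: 54 × (46 × 45)/(99 × 98) = 54 × 2070/9702 = 11.5.
- 80 + 20: 80 × (20 × 19)/(99 × 98) = 80 × 380/9702 = 3.1.

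A child with m repeats has rows under both arms within the repeat set with probability 1 − 2 × 0.5^m, which is 50% for m = 2 and 75% for m = 3.

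**4. Stay compared by arm.** Assumptions: a 0.60 SD effect, one stay value per child, each placement randomised independently 1:1, ordinary two-sample t-test, 54 + 46, 10,000 simulated trials.

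| What drives stay | Repeat set: estimate (SD), rejection | Once per child by first arm: estimate (SD), rejection |
|---|---|---|
| First arm | 0.00, 5.2% | 0.60, 56.9% |
| Average of the child's arms | 0.19, 9.8% | 0.43, 33.5% |
| Last arm | 0.32, 18.2% | 0.32, 19.5% |

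Two repeat-set results can be checked by hand. If the first arm drives stay, the repeat's arm is drawn independently of it, so the expected difference is zero. If the last arm does, only each child's final repeat row carries the relevant arm. The expected number of children with a repeat is n × r/(n+r−1) = 54 × 46/99 = 25.1, so final rows are 25.1/46 = 0.545 of the set and 0.60 × 0.545 = 0.33, close to the simulated 0.32. With 80 + 20 the repeat-set rejection rates are 4.9%, 8.6% and 16.7%. The low rates partly reflect the small set, so the shrunken estimates are the cleaner evidence. With no true effect, the repeat-set comparison rejects in 5.1% of 20,000 trials.

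**5. Time, attempts and X-rays in the repeat set.** Power at an assumed 0.5 SD effect (4,000 simulated trials for the 46-row set):

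| Within-child correlation | 46 rows: t-test | 46 rows: random intercept | 20 rows: t-test | 20 rows: random intercept |
|---|---|---|---|---|
| 0.3 | 37.1% | 40.2% | 17.4% | 16.4% |
| 0.5 | 39.6% | 47.5% | 16.6% | 16.8% |
| 0.7 | 38.0% | 62.1% | 18.1% | 21.5% |

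The random-intercept columns take the variances as known, so they are a best case; in the 46-row set Type I error was then 4.3–4.5%. With variances estimated by REML and no small-sample correction, Type I error was 5.8–6.3%. With Satterthwaite degrees of freedom it was 6.3–7.4% (1,500 trials), against 4.7–6.1% for the plain t-test in the same runs. Kenward-Roger was not checked.

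**The case against.** Several counter-arguments have weight.

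- **Initial and repeat placements are already separated.** This stands for the initial set. It does not help inside the repeat set, which the plan itself announces.
- **No comparison of stay by arm is announced in any set.** Stay is listed beside baseline descriptors such as why the child was admitted, and the hypotheses concern radiation, time and cost. This stands. Counting pre-repeat days toward the repeat's arm is therefore a gap the plan leaves open, not a rule it states.
- **Treating placements as unrelated is inferred.** It follows from the counting rule and the absence of any within-child method. The enrollment log may allow linkage, and the attached data sheet, which is not in the public text, may define stay. No described analysis uses either.
- **The chart-review mix may not transfer.** The trial takes only tubes of 8F or more and re-randomises only when a tube comes out or is pulled out. Hence the 80 + 20 case.

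Three stronger readings are tempting but unsupported.

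- **A reader might infer inflated false positives.** Each placement is randomised separately, and Type I error stays near 5%.
- **A reader might infer that initial and repeat rows will be mixed in one test.** No pooled analysis is announced, so no figure for one is given here.
- **A reader might infer that the trial is underpowered.** Power of about 70% (initial) and 63% (repeat) arises only if 40 is per arm, 100 counts placements and the 46/85 share transfers. If 100 counts children, even 40 per arm gives 92.6% for the initial analysis. If 40 is a total and 100 counts placements, power is 94.5% and 90.5%.

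**Conclusion.** The concern holds for the repeat-placement analysis and should be addressed; confidence is medium. As written, the plan lets one child's stay enter the repeat set more than once and leaves open that days before the repeat count toward its arm. The number of children entered more than once is about 11 of 54 on the chart-review mix and about 3 of 80 with fewer repeats. At an assumed 0.60 SD effect, a stay comparison there would reject in about 5% to 18% of trials, depending on which placement drives stay, which the documents do not say.

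For placement outcomes the loss is precision only. In a 46-row repeat set it is small at a within-child correlation of 0.3 and large at 0.7, measured against a best-case model; in a 20-row set there is little to gain. The initial-placement analysis is not affected by duplicate rows, and no error inflation is claimed. The unclear counting unit is a minor point, and the documents do not warrant a replacement power figure.

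**What to change.** (a) Analyse ICU stay, hospital stay and ventilator days once per child by first allocation, which is the intention-to-treat comparison, and do not compare them by arm in the repeat set. Treat time to full feeds the same way, or define it per placement with its own start.

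(b) Name the initial-placement analysis as primary. Keep a child identifier on every record. Wherever a child can have more than one row, use a within-child method, for example a random intercept with a small-sample correction whose Type I error has been checked at the expected set size.

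(c) As a minor clarification, state whether 30, 40 and 100 count children or placements, and which analysis the 86% covers.

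**Cost.** Plan wording, plus one identifier field if the data sheet lacks it. The modelling becomes slightly more complex. First allocation does not always give a strong comparison: at the assumed 0.60 SD effect its rejection rate falls from 56.9% if the first arm drives stay to 19.5% if the last arm does. It is proposed because it respects the randomisation, not because it always has more power.

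### The plan's worry that some children are not comparable is met only by an undefined PRISM 'index'; two baseline items belong in a pre-specified adjusted comparison, not among the secondary outcomes

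*Combined protocol and SAP*

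**What the plan says.** The Data Analysis Plan (Item 6) raises the issue itself. A healthy child, it says, "may not be comparable to a child with caustic ingestion or a child with history of esophageal stricture", and it adds previous esophageal surgery and severe scoliosis to the list. It promises to standardise patients within each group, and the one concrete step is that "we will index the results to the Pediatric Risk of Mortality (PRISM) score". No model, ratio, strata, scoring time or list of affected outcomes follows.

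The between-arm comparison appears only in the power statement, as "The standard (two-sided) F-test of association between CEAS and blind technique placement". That statement serves the hypothesis that "CEAS method will decrease radiation exposure, time to placement, and cost compared to the blind technique". It gives 86% power with 40 subjects at a Type I error of 0.05. The plan then says "we will enroll a minimum of 100 individuals" for each population, with a mid-study analysis at 30 patients.

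The Step-by-Step Methods (Item 6) say the team will "gather clinical data on secondary outcomes that include intensive care unit stay, hospital stay, mechanical ventilation days, reason for admission". The list continues "reason for admission and time to achieve full feeds, previous gastrointestinal (GI) procedures or surgeries". A repeat placement is re-randomised and counted as a new subject, but "we will carry out separate analysis for all subjects with initial placement and repeat placement".

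**The concern.** The conditions that worry the authors are matters of anatomy and history. PRISM is, by its name, a mortality-risk score, and the documents do not connect it to those conditions. Two analysts reading the indexing sentence could reasonably do different things: divide by the score, stratify on it, regress on it, or describe each arm separately. Because the step is described within each group, it is not clear that it touches the contrast between arms at all.

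The named data item closest to the worry is previous GI procedures or surgeries. It sits with reason for admission under secondary outcomes. Neither can be an effect of the placement method, and neither is given a part in the comparison.

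Two things are at stake. One is precision, including protection against chance imbalance in a small trial. The other is that the form of the adjustment is still open when the first 30 patients' data are examined.

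**Working it through.** **1. What the plan offers against non-comparability**

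- Design: randomisation by sealed envelopes. Item 4 relies on randomisation to remove population bias. No stratification is described.
- Eligibility (Item 5): only an open chest or abdominal wall is excluded, so the children of concern can enter.
- Analysis: the PRISM index, plus the split into initial and repeat placements. Nothing in the analysis uses anatomy or history.

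**2. The plan's own figure**

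The 86% cannot be reproduced, because no effect size, SD or allocation ratio is given. It can be solved backwards with a noncentral F test, two equal arms, alpha 0.05, df = (1, N − 2) and noncentrality N·d²/4.

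- 40 in total (20 per arm): d = 0.987.
- 40 per arm (80 in total): d = 0.688.

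Both assume that the 86% refers to a test without covariates, which the plan does not say.

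**3. Effect of adjustment on the confidence interval**

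Let R² be the share of outcome variance explained by two covariates. The documents give no value, so 0 to 30% is assumed. The ratio of adjusted to unadjusted CI half-width is approximately

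√(1 − R²) × √[(N − 3)/(N − 5)] × t(N − 4)/t(N − 2).

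The last two factors are the price of estimating two covariates:

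- N = 40: √(37/35) × 2.0281/2.0244 = 1.030
- N = 54: √(51/49) × 2.0086/2.0066 = 1.021
- N = 100: √(97/95) × 1.9850/1.9845 = 1.011

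| N | R² = 0 | 10% | 20% | 30% |
|---|---|---|---|---|
| 40 | +3.0% | −2.3% | −7.9% | −13.8% |
| 54 | +2.1% | −3.1% | −8.7% | −14.6% |
| 100 | +1.1% | −4.1% | −9.6% | −15.4% |

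Simulated regressions with a yes/no item and a skewed score agree within about 0.1 percentage points. Break-even R² is 1 − 1/1.030² = about 6% at N = 40, and 1 − 1/1.011² = about 2% at N = 100.

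The row for 54 covers the case where the 100 are placements rather than children. Item 3 reports 46 patients and 85 placements, and 46/85 = 0.54, so 100 placements would hold about 54 initial ones.

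**4. Effect on power** (same F test, d replaced by d/√(1 − R²), two fewer df)

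| Setting | Unadjusted | R² 10% | 20% | 30% |
|---|---|---|---|---|
| N = 40, d = 0.987 | 86% | 89.2% | 92.4% | 95.2% |
| N = 100, d = 0.987 | 99.8% | no material gain | | |
| N = 100, d = 0.688 | 92.6% | 94.9% | 96.8% | 98.3% |

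At N = 40, simulation that allows for estimating the covariates gives about 87%, 91% and 94%.

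**5. Chance imbalance**

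Take simple 1:1 randomisation and a baseline factor with an assumed prevalence of 10%, 20% or 30%. The chance that the arms differ by 20 percentage points or more is 6%, 16% or 23% at 20 per arm. At 50 per arm it is 0.2%, 1.7% or 3.8%.

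**6. Scale for x-rays**

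Every placement has at least one x-ray, and Item 3 gives 194/85 = 2.28 per placement. Suppose a model of x-rays beyond the first showed a ratio of 0.45 (assumed). The total would go from 2.28 to 1 + 1.28 × 0.45 = 1.58, a fall of 31%, whereas the ratio alone reads as 55%. Radiation exposure follows the total.

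**The case against.** A reader might infer that the comparison of CEAS with blind placement is biased because the children differ. The documents do not support that. Patients are randomised, so these factors balance in expectation and an unadjusted comparison is valid without any PRISM step. A reader might also infer that reason for admission and GI history will be tested as effects of placement. No section plans such a test; the list reads as items to be collected, and the fault is one of classification.

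Other objections have more force:

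- **The gain is assumed.** R² is not in the documents, and neither is the statement that 86% is unadjusted. If the 86% already allowed for two covariates with R² of 10% to 30%, the implied d at 40 in total would be 0.94 to 0.83, and unadjusted power would be 82% to 72%. This stands, so the power figures are illustrations. The CI ratios do not depend on the 86%.
- **At 100 subjects power may already be ample** (99.8% with d = 0.987). This stands; on that reading the benefit is a narrower interval.
- **The data collection sheet is attached to the form but not in the text.** It may record stricture, scoliosis or caustic ingestion. That bears on which covariates are available, but it would not define the index or give any item a role.
- **PRISM may not suit every child.** Floor and IMC patients are eligible, PRISM is not in the listed data items, and a score taken after placement is not a baseline covariate. This stands and shapes the fix.
- **Deleting the indexing sentence would also close the gap.** True, but it gives up any gain in precision and leaves the authors' own worry unanswered in the analysis.

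**Conclusion.** The point holds as a modest, inexpensive improvement. The indexing step cannot be carried out as written and does not address the between-arm contrast. Two pre-randomisation items are misclassified as outcomes and go unused. The consequence is lost precision, exposure to chance imbalance (mainly if the trial stays near 40 subjects), and an adjustment left open past the look at 30 patients. It is not a threat to validity.

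The size is a 95% CI about 4%, 10% or 15% narrower at N = 100 for an assumed R² of 10%, 20% or 30%. If the covariates explain nothing, it is about 1% wider at N = 100 or 3% wider at N = 40. These figures assume equal arms, a continuous outcome and two covariates. The textual finding does not depend on them.

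**What to change.** Replace the indexing sentence with one between-arm regression, fixed before the look at 30 patients:

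- Regress each placement outcome on arm, with previous GI procedure or surgery and PRISM as covariates. State that PRISM is scored before placement. If it will not be available for floor and IMC children, adjust for the GI item alone.
- Fit the model to initial placements, and keep repeat placements in their separate analysis.
- Report the adjusted difference with its 95% CI beside the unadjusted result.
- Report total x-rays per placement and cost as differences in arithmetic means. A ratio of x-rays beyond the first, or a difference in log cost, would answer a different question from radiation exposure and cost-effectiveness.
- Move reason for admission and previous GI procedures or surgeries to the baseline variables. Consider reason for admission as a further covariate if it identifies the conditions the plan names.

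The cost is mainly plan wording, because the plan already names both covariates; confirming that PRISM can be scored before placement outside the ICU is the one practical check. The statistical downside is the slight CI widening given above if the covariates are uninformative. The two covariates answer the stated worry only in part: GI history will not capture scoliosis, nor caustic ingestion or a stricture without a procedure.
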